5.1. Summary of Study Design

Study J2T-MC-KGAK (KGAK) (also known as DRM06-AD18) is a randomized, double-blind, placebo-controlled, parallel-group study to assess the impact of lebrikizumab on vaccine responses in adult participants (18 to 55 years) with moderate-to-severe atopic dermatitis (AD). Approximately 240 participants will be enrolled into the study. The study has 1 treatment period (16-week). Participants completing this 16-week study will be offered continued treatment in a separate long-term extension study, J2T-DM-KGAA (DRM06-AD07). Participants who early terminate or choose not to enter the long-term extension study will undergo a follow-up visit approximately 12 weeks after the last study drug injection for safety follow-up.

5.1.1. Screening Period

Screening Period: Participants will be evaluated for study eligibility before the Baseline Visit (Day 1). Electronic diary collection will begin at screening.

5.1.2. Baseline and Double-Blinded Treatment Period (Week 0 to Week 16)

Participants found to be eligible according to all of the study entry criteria will be randomly assigned in a 1:1 ratio to receive either lebrikizumab or placebo. The treatment groups in the Blinded Treatment Period are

- Lebrikizumab 250 mg every 2 weeks (Q2W): 500 mg lebrikizumab administered at baseline and Week 2 (loading dose; 2 prefilled syringes with a pre-filled syringe needle safety device [PFS-NSD]) and 250 mg Q2W through Week 14
- Placebo: 4 mL (2 PFS-NSD) administered at baseline and Week 2 and 2 mL Q2W through Week 14

At Week 12, after the predose vaccine titers have been drawn, 1 dose of each of the 2 commercially available vaccines will be administered to all participants still on study drug:

[figure not shown]
- Diphtheria and Tetanus Toxoids and Acellular Pertussis Vaccine Adsorbed (Tdap)
- Meningococcal (Groups A, C, Y, and W-135) Oligosaccharide Diphtheria CRM197 Conjugate Vaccine (MCV)

Participants whose study drug has been permanently discontinued before Week 12 will not receive the vaccines.

5.1.3. Safety Follow-up Visit

Participants who terminate early from the study or do not enroll in the long-term extension study, J2T-DM-KGAA (DRM06-AD07), will undergo a follow up visit approximately 12 weeks after the last study drug injection.

Figure KGAK.5.1 illustrates the study design.

Abbreviations: MCV = Meningococcal (Groups A, C, Y, and W-135) Oligosaccharide Diphtheria CRM197 Conjugate Vaccine; N = number of planned randomized patients; n = number of planned randomized patients at each arm; Q2W = every 2 weeks; Tdap = Diphtheria and Tetanus Toxoids and Acellular Pertussis Adsorbed.

Figure KGAK.5.1. Illustration of study design for Protocol KGAK.

5.2. Determination of Sample Size

Approximately 240 participants will be randomly assigned to study intervention (1:1 ratio for lebrikizumab:placebo) such that approximately 218 evaluable per protocol (PP) participants complete the study.

The sample size for this study was determined based on the following information:

- The percentage of study participants with positive response to the tetanus vaccination at Week 16 is 83.7% and 83.3% for active treatment and placebo, respectively (Blauvelt et al. 2019)
- The percentage of study participants with rabbit complement serum bactericidal assay (rSBA)-Meningococcal C total seroresponse at Day 29 is 90% (Tipton et al. 2019, adjusted for adult population)

Assuming the observed booster response to tetanus toxoid for both lebrikizumab and placebo is 83% at Week 16, with 109 participants per arm, the Wald 2-sided 90% confidence interval (CI) for the difference in booster response is (-0.08, 0.08).

Similarly, assuming the positive antibody response to MCV for both lebrikizumab and placebo is 90% at Week 16, with 109 participants per arm, the Wald 2-sided 90% CI for the difference in booster response is (-0.07, 0.07).

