9.1. Statistical Hypotheses

Study KGAK is a descriptive study with no planned hypothesis testing. Confidence intervals (CIs) will be used to compare seroresponses for lebrikizumab- and placebo-treated participants.

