9.2. Sample Size Determination

Approximately 240 participants will be randomly assigned to study intervention (1:1 ratio for lebrikizumab:placebo) such that approximately 218 evaluable per protocol (PP) participants complete the study.

The sample size for this study was determined based on the following information:

- The percentage of study participants with positive response to the tetanus vaccination at Week 16 is 83.7% and 83.3% for active treatment and placebo, respectively (Blauvelt et al. 2019).
- The percentage of study participants with human complement serum bactericidal assay (hSBA)-Meningococcal C total seroresponse at Day 29 is 90% (Tipton et al. 2019, adjusted for adult population).

Assuming the observed booster response to tetanus toxoid for both lebrikizumab and placebo is 83% at Week 16, with 109 participants per arm, the Wald 2-sided 90% CI for the difference in booster response is (-0.08, 0.08).

Similarly, assuming the positive antibody response to MCV for both lebrikizumab and placebo is 90% at Week 16, with 109 participants per arm, the Wald 2-sided 90% CI for the difference in booster response is (-0.07, 0.07).

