Abbreviations: AD = atopic dermatitis; ADA = antidrug antibody; AE = adverse event; EASI = Eczema Area and Severity Index; EASI 90 = $\geq 90\%$ reduction from baseline in EASI score; eCRF = electronic case report form; hSBA = human complement serum bactericidal assay; ICH = International Council for Harmonisation; IgG = immunoglobulin G; ITT = intent-to-treat; MCMC-MI = Markov chain Monte Carlo multiple imputation; mITT = modified intent-to-treat; NRS = numerical rating scale; POEM = Patient-Oriented Eczema Measure; PPS = per-protocol set; PROMIS = Patient-Reported Outcomes Measurement Information System; PSAP = program safety analysis plan; TE-ADA = treatment-emergent antidrug antibody.

SAP Version 3 was approved after Week 16 database lock (DBL) and before final DBL.

Revisions in SAP Version 3 include:

Section	Description of Change	Rationale
Sections 4, 5.2, 6.10, 6.10.1	Replaced hSBA with rSBA.	At the time of Week 16 DBL, the MCV hSBA data collected and processed by Eurofins was considered invalid because the assay procedure was not successfully validated. Personnel who have access to the patient-level data have no access to the biospecimen for the MCV hSBA. For final analysis, Lilly has identified Nexelis as an alternate vendor for analyzing the MCV response using a fully validated rSBA to deliver results for the final DBL and for analysis.
Section 6.16	Added detailed description of MCV response data issue observed at Week 16 DBL. Added the solution of MCV response data issue and discussed the impact to Week 16 DBL and final DBL.	The same as above.

Abbreviations: DBL = database lock; hSBA = human complement serum bactericidal assay; MCV = Meningococcal (Groups A, C, Y, and W-135) Oligosaccharide Diphtheria CRM197 Conjugate Vaccine; rSBA = rabbit complement serum bactericidal assay.

4. Study Objectives

Table KGAK.4.1 shows the protocol-defined objectives and endpoints of the study. In addition, the analysis of some nonprotocol-defined endpoints is described in Section 6.10 to provide supportive evidence of efficacy.

Table KGAK.4.1. Protocol-Defined Objectives and Endpoints

Objectives	Endpoints
Primary	

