
 To compare the seroresponses to the Tdap and MCV between lebrikizumab-treated and placebo-treated participants with moderate to severe AD 	
The percentage of participants who:
 
 1. Develop a booster response to tetanus toxoid 4 weeks after the administration of the Tdap vaccine (Week 16) Booster response is defined as: 
 ○ ≥ 4-fold increase in antitetanus IgG antibody concentration if the prevaccination level was >0.10 IU/mL and ≤ 2.7 IU/mL; OR ○ ≥ 2-fold increase in antitetanus IgG antibody concentration if the prevaccination level was >2.7 IU/mL; OR ○ ≥ 4-fold increase in antitetanus IgG antibody concentration and a postvaccination level ≥ 0.10 IU/mL if the prevaccination level was ≤ 0.10 IU/mL 2. Have positive antibody response to Meningococcus C antigen of the MCV 4 weeks after the administration of the vaccine (Week 16) Positive antibody response to Meningococcus C antigen of the MCV is defined as: 
 ○ postvaccination rSBA titer ≥ 4 times the LLOQ, if the prevaccination rSBA titer is less than the LLOQ; OR ○ postvaccination rSBA titer ≥ 4 times the prevaccination titer, if the prevaccination rSBA titer is greater than or equal to the LLOQ

Objectives	Endpoints
Secondary	

 To compare the efficacy of lebrikizumab with that of placebo in the treatment of patients with moderate-to-severe AD To compare the patient-reported outcomes between lebrikizumab-treated and placebo-treated participants with moderate-to-severe AD 	
Percentage of participants at Week 16
 
 with an IGA score of 0 or 1 and a reduction of ≥ 2 points from baseline achieving EASI 75 achieving EASI 90 achieving ≥ 4-point improvement from baseline in Pruritus NRS score who had baseline Pruritus NRS ≥ 4 
Percentage change from baseline to Week 16 in
 
 EASI Pruritus NRS 
Change from baseline to Week 16 in
 
 BSA Sleep-loss score

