Week 16 DBL: An unblinded interim analysis will be performed at the time (that is, a cut-off date) the last participant completes Week 16 or the ETV from the study. At the time of Week 16 DBL, the primary endpoint analysis related to booster response to tetanus toxoid has been performed. At the time of Week 16 DBL, the MCV hSBA data is considered as invalid because the assay procedure was not successfully validated at Eurofins Scientific®. Only a small group of statisticians working on the data analysis at the time of the Week 16 DBL had access to the patient-level data. A small internal group of Lilly personnel have been unblinded with a high-level summary result including Global Patient Safety and Medical study team representatives. The patient-level data was quarantined once MCV issues were identified. Personnel who have access to the patient-level data have no access to the biospecimen for the MCV hSBA. The primary endpoint analysis related to MCV response will be on hold until final DBL.

The study will not be terminated early on the basis of efficacy following these interim analyses.

Final DBL: A final DBL will occur after all participants have completed the safety follow-up period of the study, discontinued current study, or enrolled into the long-term extension study DRM06-AD07.

Lilly identified Nixelis as an alternate vendor for analyzing the MCV response using a fully validated rabbit complement serum bactericidal assay (rSBA) in order to deliver results for the final DBL and for analysis. The final DBL will include all data collected by the date of final DBL except Eurofins hSBA data. Final DBL will not occur until new fully validated rSBA is completed by Nixelis and all MCV response data is transferred. The primary endpoint analysis related to booster response to tetanus toxoid will be performed with the Eurofins Tdap data that

is a retransfer of the Week 16 DBL Eurofins Tdap data. The primary endpoint analysis related to MCV response will be performed with the Nexelis retested rSBA data based on the biospecimen collected through Week 16 DBL. For other efficacy and safety analysis, all data collected by the date of final DBL will be included.

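### Does naming rSBA behind the 90% Meningococcal C planning rate in SAP 5.2 undermine the stated precision of about ±7 points?

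*SAP*

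**What the plan says.** Protocol Section 9.2 plans about 240 randomized participants to obtain about 218 evaluable, or 109 per arm. For the meningococcal co-primary endpoint it takes the rate from a published booster-dose study, adjusted for adults: "human complement serum bactericidal assay (hSBA)-Meningococcal C total seroresponse at Day 29 is 90" percent.

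SAP Section 5.2 repeats this with the same rate, day, source and adjustment, but reads "rabbit complement serum bactericidal assay (rSBA)-Meningococcal C total seroresponse at Day 29 is 90" percent.

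Both documents then suppose a 90% response to the meningococcal vaccine in each arm, with 109 per arm, and reach the same result: "the Wald 2-sided 90% CI for the difference in booster response is (-0.07, 0.07"). That sentence refers to the vaccine and not to an assay.

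The SAP explains where rSBA came from. Section 3 (Revision History) says "SAP Version 3 was approved after Week 16 database lock (DBL) and before final DBL". It lists Sections 4, 5.2, 6.10 and 6.10.1 as the places where the assay term was replaced, because the hSBA procedure had not been successfully validated. Section 6.16 adds: "The primary endpoint analysis related to MCV response will be performed with the Nexelis retested rSBA data".

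On inference, Protocol Section 9.1 is explicit: "Study KGAK is a descriptive study with no planned hypothesis testing".

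**The concern.** One published rate is assigned to two different assays in two current documents. The SAP presents the rSBA rate as what the sample size was determined from, although rSBA was adopted after the Week 16 lock. Neither the revision history nor Section 6.16 gives an rSBA response rate, a bridge between the assays or a recalculation.

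The responder definition in Table KGAK.4.1 depends on the assay's own lower limit of quantitation, with one branch applying "if the prevaccination rSBA titer is less than the LLOQ". The response rate under rSBA therefore need not equal the rate under hSBA.

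The study tests no hypothesis, so expected interval width is the only numerical support for 109 per arm. A reader could take ±7 points as the precision planned for the assay now analysed, when the protocol supports it only for hSBA. If the rSBA rate were well away from 90%, the expected width would differ, and the direction is unknown.

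**Working it through.** **Inputs.** From Protocol 9.2 and SAP 5.2: 109 evaluable per arm, a two-sided 90% Wald interval (z = 1.645), a common response of 0.90 for the meningococcal vaccine and 0.83 for tetanus, and a true difference of zero.

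**Formula.** Half-width = z × sqrt(2p(1 − p)/n).

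**Reproducing the plan's figures.**

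- Meningococcal: 1.645 × sqrt(2 × 0.90 × 0.10 / 109) = 0.0668, which rounds to the stated 0.07.
- Tetanus: 1.645 × sqrt(2 × 0.83 × 0.17 / 109) = 0.0837, which rounds to the stated 0.08.

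Both intervals are right as computed. The unstratified Newcombe half-width at 90% in each arm is 0.069, so the Wald approximation is not hiding anything.

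**Sensitivity to the unknown rSBA rate.** The documents give no such rate, so the values of p below are assumptions on both sides of 90%.

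| Assumed common response | 90% Wald half-width, 109 per arm |
|---|---|
| 98% | 0.031 |
| 95% | 0.049 |
| 90% (plan) | 0.067 |
| 85% | 0.080 |
| 83% (tetanus planning rate) | 0.084 |
| 80% | 0.089 |
| 70% | 0.102 |
| 50% (maximum) | 0.111 |

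The half-width rounds to 0.07 only for a common response of about 87.0% to 90.6%. A higher rate gives a narrower interval than stated, and a lower rate a wider one.

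**Comparison with the other co-primary endpoint.** Tetanus sets the wider planned interval. For any common rSBA response of 83% or more, the meningococcal half-width is at most the 0.084 that the plan already accepts. Even at 50% the excess is 0.1114 − 0.0837 = 0.0277, under 3 percentage points.

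**Timing.** Section 6.16 places the Week 16 cut-off at the last participant's Week 16 or early termination visit. Version 3 came after that lock, and the rSBA retest uses specimens collected through it. The number randomized was therefore fixed before rSBA entered the SAP.

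**What is reported.** SAP Section 6.10.1 and Table KGAK.6.7 specify a 90% stratified Newcombe interval, by baseline IGA severity, from the observed responses. The planning rate does not enter that calculation.

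**The case for a change.** The strongest case for a change is that this is a false statement about the past in a section whose only job is to justify the sample size. With no hypothesis test there is no power calculation to fall back on. The SAP discloses the assay switch, but nowhere says that the 90% was originally an hSBA rate, and Section 5.2 as it stands says otherwise. Even if the cited study also reports rSBA results, which cannot be checked from these documents, the protocol shows that the planning rate was read as hSBA. Table KGAK.4.1 has a related blemish: the SAP says "Table KGAK.4.1 shows the protocol-defined objectives and endpoints of the study", yet the table shows rSBA where the protocol defines hSBA.

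Two parts of this stand. The assay label in the bullet is wrong as history, and the mismatch is between two current texts rather than with superseded wording.

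The consequence does not stand. The interval sentence is a conditional statement that holds for any assay with 90% response in both arms. The revision history names Section 5.2 among the sections where the term was replaced and gives the reason, so a reader comparing the documents can see what happened. Recomputing planned precision after the lock, from a rate the documents do not contain, would add a grid of assumptions and no information about the trial. The heading of Table KGAK.4.1 is a separate labelling matter and does not affect the sample size.

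**Conclusion.** This is a clerical slip, and no change to the plan follows. A term replacement suited to the endpoint definition also reached a sentence about how the sample size had been set. The 90% is documented in the protocol as an hSBA rate and should be read that way.

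No stated number is shown to be wrong. The interval reproduces at a half-width of 0.067. Across all possible common response rates the half-width cannot exceed 0.111 at 109 per arm, and at 83% or more it stays within the 0.084 accepted for tetanus. These figures assume equal response in the two arms and the planned 109 evaluable per arm. The rSBA rate itself is unknown from the documents.

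The number randomized was fixed, the specimens were already collected, and no margin, power or stopping decision rests on the figure. The observed stratified Newcombe interval will show the precision actually achieved with rSBA. Relabelling the bullet would tidy the record but would change neither what the trial does nor what it can conclude.

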5.3. Method of Assignment to Treatment

Assignment to treatment groups will be determined by a computer generated random sequence using an interactive web-response system (IWRS). All participants will be randomly allocated to receive the study treatment using IWRS at the baseline visit. The allocation to treatment will be prospectively stratified by disease severity (Investigator's Global Assessment [IGA] 3 versus 4). At the baseline visit (Day 1), once a participant is considered eligible to participate in the study, demographic and stratification information will be entered into the Electronic Data Capture

(EDC) system. Site personnel will confirm that they have located the correct kit by entering a confirmation number found on the kit into the IWRS.

6. A Priori Statistical Methods

6.1. General Considerations

Statistical analysis of this study will be the responsibility of Eli Lilly and Company (Lilly). The latest version of the Medical Dictionary for Regulatory Activities (MedDRA) will be used.

Analyses and summaries from the assessment of endpoints described in the protocol (for example, described in KGAK Synopsis Objectives and Endpoints) are planned to be included in a clinical study report (CSR). Analyses and summaries for key safety data are also planned to be included in the CSR. Results from additional efficacy analysis and other safety analyses may also be provided in the CSR as deemed appropriate.

Any change to the data analysis methods described in the protocol will require a protocol amendment ONLY if it changes a principal feature of the protocol. Any other change to the data analysis methods described in the protocol and the justification for making the change will be described in the CSR.

All statistical processing will be performed using SAS® unless otherwise stated. Some of the analyses described in this document will be incorporated into interactive display tools instead of or in addition to static displays. Except where noted, all statistical tests will be 2-sided and will be performed at the 0.05 level of significance.

The Schedule of Visits and Procedures outlined in the protocol specifies the allowable windows for assessments. Assessments performed outside these windows will not be excluded from any analysis, unless specified otherwise.

6.1.1. Analysis Populations

Analysis populations are defined in [Table KGAK.6.1](#) along with the analysis they will be used to conduct. [Table KGAK.6.2](#) describes the treatment groups and the comparisons for each study period and the analysis population.

Table KGAK.6.1. Analysis Populations

Population	Description
All Entered Patients	All participants who signed informed consent. Participant flow will be summarized.
Intent-to-Treat (ITT) Population	All randomized participants, even if the participant does not take the assigned treatment, does not receive the correct treatment, or otherwise does not follow the protocol. Participants will be analyzed according to the treatment to which they were assigned.
Modified Intent-to-Treat (mITT) Population	ITT population excluding all participants from Site 1883 ^a and Site 1827 ^b . Unless otherwise specified, efficacy and health outcomes analyses will be conducted on this population.
Safety Population	All randomized participants who received at least 1 dose of study treatment.
Modified Safety Population	Safety population excluding all participants from Site 1883 and Site 1827. Safety analyses will be conducted on this population.
Per-Protocol Set (PPS)	All Safety Population participants without any significant protocol deviations. Significant protocol deviations include (but not limited to) the following:

Population	Description
	
 Used prohibited treatment that required permanent discontinuation of the study drug (see Protocol Section 7.1.2) that is systemic rescue medication Missed either 1 or both Week 12 or Week 16 study visits (Visits 8 and 10) Had not been compliant with the dosing regimen (i.e., participants must receive 80% of the expected injections of study drug and both of the vaccines during participation in the study) Exceeded the out-of-the-visit window at the Week 16 visit (Visit 10) by more than 7 days 
Additional significant protocol deviations that could possibly have impact on precise evaluation of the primary objective will be recorded in a separate tracker and participants with these significant protocol deviations will also be excluded from the PPS.
 
Primary analyses for vaccine response primary endpoints will use the PPS. Analyses for IGA0/1 and EASI 75 will be repeated using the PPS.

Abbreviations: EASI = Eczema Area and Severity Index; EASI 75 = $\geq 75\%$ reduction from baseline in EASI score; IGA = Investigator's Global Assessment.

- a The rationale for excluding participants from Site 1883 is in a directed site audit triggered by statistically implausible data in Study KGAD/AD06 at this study site, and the same site was also included in this study, KGAK/AD18. It was determined that some or all of the study participants at this site did not meet the eligibility criterion of having moderate-to-severe atopic dermatitis, and associated data was unreliable.
- b The rationale for excluding participants from Site 1827 is a clinical site audit of lebrikizumab atopic dermatitis studies KGAK/AD18 and KGAA/AD07 at this site resulted in critical findings. It was determined by the audit that there was a lack of source documentation needed to substantiate eligibility for all participants enrolled at this site. Additionally, a quality issue was opened that participant data regarding their moderate-to-severe atopic dermatitis is either unreliable, inconsistent, and/or missing source documentation.

Table KGAK.6.2. Treatment Groups and Comparisons and Analysis Population

Study Period	Analysis Population	Treatment Groups	Abbreviation	Inferential Comparisons When Applicable
Treatment Period	mITT; Safety; Modified Safety; PPS	Placebo; Lebrikizumab 250 mg Q2W	PBO; LEB250Q2W	LEB250Q2W vs PBO

Abbreviations: LEB = lebrikizumab; mITT = modified intent-to-treat; PBO = placebo; PPS = per protocol set; Q2W = every 2 weeks; vs = versus.

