Table KGAK.6.8. Summary Tables/Listing Related to Adverse Events	46
Table KGAK.6.9. Analysis for Clinical Laboratory Evaluations	47
Table KGAK.6.10. Analysis Related to Vital Signs	48
Table KGAK.6.11. Summary Tables Related to Hepatic Safety	49
Table KGAK.6.12. Summary Tables Related to Eosinophilia and Eosinophil-Related AE	50
Table KGAK.6.13. Summary Tables/Listing Related to Infection Related AE	50
Table KGAK.6.14. Summary Tables/Listing Related to Conjunctivitis.....	50
Table KGAK.6.15. Summary Tables/Listing Related to Hypersensitivity	51
Table KGAK.6.16. Summary Tables Related to Injection Site Reactions.....	51
Table KGAK.6.17. Summary Tables Related to Malignancies	51
Table KGAK.6.18. Summary Tables Related to Atopic Dermatitis Exacerbation	52
Table KGAK.6.19. Summary Tables Related to Suicide/Self-injury	52

Table of Contents

Figure	Page
Figure KGAK.5.1. Illustration of study design for Protocol KGAK.....	17

Table of Contents

Appendix		Page
Appendix 1.	Study Visit Mapping for Pruritus NRS, Skin Pain NRS, Sleep-loss Diary and POEM.....	60
Appendix 2.	Definition of Rescue Medications.....	61
Appendix 3.	Details of Combining Estimates and Test Statistics for Categorical Endpoints with Multiple Imputation	62

3. Revision History

Statistical Analysis Plan (SAP) Version 1 was approved on 16 November 2020 prior to any unblinding on 16 November 2020.

SAP Version 2 was approved on 01 March 2022 prior to unblinding of Week 16 database lock (DBL). Revisions in SAP Version 2 included:

Section	Description of Change	Rationale
Section 4	Reworded the language of secondary objectives.	To be consistent with protocol language.
Section 4	Added exploratory section in Table KGAK.4.1.	To provide details about the exploratory analysis.
Section 6.1.1, Table KGAK.6.1	
Added 2 analysis populations (mITT and Modified Safety Population).
 
Removed “Unless otherwise specified, efficacy and health outcomes analyses will be conducted on this population” from the ITT population part.
 
Removed “Safety analyses will be conducted on this population.” from the Safety Population part.
 
Reworded PPS population part.
	
See footnote of Table KGAK.6.1.
 
To be consistent with protocol language and provide more details about how to record the additional significant protocol deviations that could possibly have impact on precise evaluation of the primary objective.

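### The per-protocol set, primary for both vaccine endpoints, is built on the unmodified Safety Population, so its stated rule does not remove the two audit-failed sites that the mITT and Modified Safety populations drop by name.

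*SAP*

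**What the plan says.** SAP Table KGAK.6.1 defines the Safety Population (all randomized and dosed) and the Modified Safety Population as separate terms. The latter is the "Safety population excluding all participants from Site 1883 and Site 1827". The mITT is the ITT population with the same two sites removed. The table's footnotes give the reasons. At Site 1883 the audit determined that "some or all of the study participants at this site did not meet the eligibility criterion of having moderate-to-severe atopic dermatitis" and that the associated data were unreliable. At Site 1827 it found a "lack of source documentation needed to substantiate eligibility for all participants enrolled at this site", and a quality issue was opened on the disease data.

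The PPS row starts from the unmodified term: "All Safety Population participants without any significant protocol deviations". It lists four deviations: systemic rescue requiring permanent discontinuation, a missed Week 12 or Week 16 visit, dosing or vaccine non-compliance, and a Week 16 visit too far out of window. The list is expressly open. Further deviations that could affect evaluation of the primary objective are to be "recorded in a separate tracker and participants with these significant protocol deviations will also be excluded from the PPS".

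The PPS is primary for both vaccine endpoints; the mITT is supplementary for them (Table KGAK.6.7). The PPS row also states: "Analyses for IGA0/1 and EASI 75 will be repeated using the PPS". Section 6.15 names eligibility violations as a possible important deviation and leaves PP exclusion to the Trial Issues Management Plan, but confines PP exclusion to a subset of deviations arising in the Treatment Period.

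**The concern.** The SAP decided that two sites could not be trusted and wrote that decision into the supplementary population for the co-primaries, but not into the primary one. Under SAP 6.2.1 the primary estimand handles intercurrent events only through the PPS definition, so membership of the PPS determines the primary result. The primary objective concerns patients with moderate-to-severe atopic dermatitis, which is what the audits found unmet or unsubstantiated.

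Three things are at stake.

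- **Population.** The primary analysis may include participants dropped elsewhere as unreliable.
- **Interpretation.** A difference between the PPS and mITT results could reflect site exclusion as well as adherence.
- **Use of the audited severity data.** They enter the PPS repeats of IGA 0/1 and EASI 75, and they supply the baseline IGA stratum in the Newcombe interval for both co-primaries.

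**Working it through.** **Step 1: the rules side by side (SAP Table KGAK.6.1).**

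| Population | Starts from | Sites 1883 and 1827 removed by name? | Role for the co-primaries |
|---|---|---|---|
| mITT | ITT | Yes | Supplementary |
| Modified Safety | Safety | Yes | None |
| PPS | Safety | No | Primary |

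An adherent, dosed participant at either site who attends Weeks 12 and 16 in window and receives both vaccines meets all four listed PPS criteria and is not in the mITT. The PPS is therefore not a subset of the mITT under the listed criteria.

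**Step 2: can another route remove them?** There are two, and neither document is reproduced in the SAP.

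- The tracker acts on deviations that could affect evaluation of the primary objective. Someone could reasonably decide that a skin-disease eligibility failure does not affect an antibody titre.
- The Management Plan acts through Section 6.15. Any participant-by-participant route may also stop short at Site 1883, where the footnote leaves open that only some participants were ineligible, while the mITT drops the whole site.

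Section 6.15 is itself ambiguous on timing. SAP 6.1.2 starts the treatment period after the first injection. Protocol 4.1 (Visits 2 to 10) and the SAP 5.1.2 heading (from Week 0) take in the baseline visit, where the IGA, EASI and BSA entry criteria are checked (Protocol 5.1). The tracker rule has no such time limit.

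**Step 3: cost in precision.** Inputs are from SAP 5.2: 109 per arm, 83% tetanus response and 90% MCV response in both arms, two-sided 90% Wald interval.

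Half-width = 1.645 × √(2p(1−p)/n)

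- Tetanus: 1.645 × √(2 × 0.83 × 0.17 / 109) = 0.0837, which rounds to the stated 0.08.
- MCV: 1.645 × √(2 × 0.90 × 0.10 / 109) = 0.0668, which rounds to the stated 0.07.

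The documents give no site counts. Assume 2, 5 or 10 fewer per arm (1.8%, 4.6% or 9.2% of 109), with 24 fewer as a stress case. Half-widths in percentage points, with unstratified Newcombe as a check because the planned method is stratified Newcombe:

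| n per arm | Tetanus Wald | Tetanus Newcombe | MCV Wald | MCV Newcombe |
|---|---|---|---|---|
| 109 | 8.37 | 8.42 | 6.68 | 6.88 |
| 107 | 8.45 | 8.50 | 6.75 | 6.95 |
| 104 | 8.57 | 8.62 | 6.84 | 7.05 |
| 99 | 8.78 | 8.84 | 7.01 | 7.24 |
| 85 | 9.48 | 9.55 | 7.57 | 7.85 |

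At 10 fewer per arm the Wald loss is 8.78 − 8.37 = 0.41 points for tetanus and 7.01 − 6.68 = 0.33 for MCV (Newcombe 0.42 and 0.36). At 24 fewer the Wald loss is 9.48 − 8.37 = 1.11 and 7.57 − 6.68 = 0.89.

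**The case against.** The strongest reply is that the PPS rule is more than its four bullets. The list is open, and exclusion for a tracker deviation is mandatory. Protocol 9.3 defines a significant deviation broadly enough to reach site-level failures, and Section 6.15 gives eligibility violations as its first example. The revision history says the PPS row was reworded in the same Version 2 that added the modified populations, citing protocol consistency and the recording of additional deviations, so the Safety Population base may be deliberate.

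This stands in part. It shows that the sites may have been removed, and that an oversight is not proven. It does not show that they were removed: the rewording does not mention them, and both routes rest on judgement and on documents outside the SAP.

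The second reply is that little follows for the co-primaries. The endpoints are designated-laboratory assays, the study is descriptive with no planned hypothesis test (Protocol 9.1), and an mITT analysis without the two sites is already planned. Randomization was stratified on the recorded IGA, so a mislabelled stratum does not by itself bias the within-stratum comparison. All of this is accepted, and it is why no bias is claimed. It does not explain why the primary population should follow a weaker site rule than the supplementary one.

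The third reply is that tetanus has already been analysed unblinded, so re-basing the PPS now is a post-unblinding change for that endpoint unless the tracker already did it. This also stands, and the fix has to deal with it openly.

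**Conclusion.** The concern holds as a defect in the stated rule. The PPS is tied to the unmodified Safety Population, no listed criterion removes Sites 1883 and 1827, and neither document says that they are excluded from it. This conflicts with the SAP's own judgement that data from these sites are unreliable.

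It is not established that participants from the two sites were analysed in the PPS; that depends on the tracker and the Management Plan. The effect on either co-primary is unknown because site enrolment is not given. The precision cost of about 0.4 points or less assumes at most 10 fewer per arm, removed equally. SAP 6.5 refers to a large number of sites, which makes a modest share plausible but does not bound it; at 24 fewer per arm the cost is about 1.1 points. The point should be fixed before the final analysis.

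**What to change.** 1. **Table KGAK.6.1.** Define the PPS as all Modified Safety Population participants without any significant protocol deviation, and state that the PPS is a subset of the mITT. Cite the site decision recorded in SAP Version 2, approved on 01 March 2022 before the Week 16 unblinding.
2. **Section 6.15.** Reconcile the Treatment Period limit with the tracker rule by stating whether eligibility or source-document failures found at or before the baseline visit can exclude a participant from the PPS.
3. **Section 6.16.** State whether the PPS used for tetanus at the Week 16 lock included the two sites. If it did, keep that result, label it, and show the re-run beside it. If the tracker or Management Plan had already removed both sites, say so; the new wording then only records the fact.

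The cost is a sentence in each place, one population flag, a slightly smaller PPS and a slightly wider interval. Because Protocol 9.3 also bases the PP population on the safety population, the departure and its reason belong in the clinical study report under SAP 6.1. The sponsor should also record whether it regards the primary-analysis population as a principal feature, since that section would then require a protocol amendment. The MCV analysis is on hold until the final lock, so only tetanus may need a labelled re-run.
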